7.3 Description of the traceability elements that accompagny the experimental medication

The modality of traceability elements that accompagny the experimental medication are in the "pharmaceutical circuit".

7.4 Authorised and prohibited treatments (medicinal, non medicinal, surgical), including rescue medications

7.4.1. Authorised rescue medication in the control group

In the control group, atM2, corticosteroid treatment (4 months of treatment, same protocol of experimental group) should be administred in case of rapid deterioration of renal function (i.e. eGFR (CKD-EPI formula) is < 70% of initial eGFR). Before corticosteroid administration, eGFR will be re-evaluated on a second sample, within an interval of at least 14 days.

At 4 months, rescue corticosteroid treatment (4 months of treatment, same protocol of experimental group) could be administred in case of failure defined by:

- PCR > 0.75 g/g
- or PCR > 0.5 g/g and >30% of initial PCR
- or eGFR (CKD-EPI formula) < 80% of initial eGFR,

In case of failure, before corticosteroid administration, proteinuria and eGFR will be reevaluated on a second sample, within an interval of at least 14 days.

At 6, 9, 12, or 18 months, rescue corticosteroid treatment (4 months of treatment, same protocol of experimental group) should be administred in case of failure defined by:

- PCR > 0.75 g/g
- or PCR > 0.5 g/g and >30% of initial PCR
- or eGFR (CKD-EPI formula) < 80% of initial eGFR,

In case of failure, before corticosteroid administration, proteinuria and eGFR will be reevaluated on a second sample, within an interval of at least 14 days.

7.4.2. Prohibited treatments

No treatments are prohibited, except from those contra-indicated with the use of corticosteroids (cf SmPC). A patient have already received a corticosteroid treatment, he should not receive a new corticotherapy.

7.5 Methods for monitoring compliance with the treatment

Compliance is evaluated orally by the patient physician at each visit with the "patient pad" and by the RCA during the monitoring of the pharmacy of each centre.

8 ASSESSMENT OF EFFICACY

Proteinuria/creatininuria ratio (PCR) and eGFR (CKD-EPI formula) evaluation

Serum creatinine will be evaluated with an enzymatic IDMS-traceable assay. Urinary protein, creatinine, sodium and urea will be evaluated on a 24-hour urinary collection (or urinary sample) at each visit.

Biochemistry analyses can be performed in private practice laboratories.

In case of failure, Proteinuria and eGFR will be re-evaluated on a second sample, within an interval of at least 14 days. For each visit, the final GFR and PCR value will be calculated from the second dosage.

Histological lesions evaluation

Renal biopsy will be performed and processed according to local practices. Histologic assessment will be performed according to the Oxford criteria studies. For patient inclusion, each inclusion criterium (mesangial proliferation, endocapillary proliferation, focal segmental glomerulosclerosis, tubular atrophy/interstitial fibrosis, cellular/fibrocellular crescents) will be scored by local pathologists. Secondarily, all renal biopsies will be re-evaluated *a posteriori* in the Necker pathology department.

Measured GFR evolution will be evaluated as follows:

mGFR will be performed according to local practice (iohexol clearance, inuline clearance, CrEDTA clearance, ...).

Given that the randomization is stratified by centre, the difference between the mGFR techniques should not have a major effect in data interpretation.

Identification of prognosis markers of failure at 24 months:

These factors will include (but are not restrited to):

- clinical factors (blood pressure, history of macroscopic haematuria, familial history of IgAN),
- biological factors (initial and time-average proteinuria, initial eGFR, time-average sodium chloride consumption),
- renal histological lesions evaluated *a posteriori* (oxford criteria, thrombotic microangiopathy, focal segmental glomerulosclerosis with features of podocytopathy)

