4.1.2 Secondary assessment criteria

Failure at 6 months will be defined as:

- PCR > 0.75 g/g
- or PCR > 0.5 g/g and > 30% of initial PCR
- or eGFR < 80% of initial eGFR
- or ESRD
- or renal transplantation
- or death.

Failure at 12 months will be defined as:

- PCR > 0.75 g/g
- or PCR > 0.5 g/g and > 30% of initial PCR
- or mGFR < 80% of initial mGFR (or eGFR if unavailable)
- or ESRD
- or renal transplantation
- or death.

Histological lesions evolution at 12 months :

The evolution of histological lesions will be assessed as the proportion of patients of both therapeutic groups with persistent severe histological lesions in repeat kidney biopsy at 12 months.

GFR evolution (mGFR or eGFR if unavailable):

The evolution of GFR at 12 and 24 months will be assessed as:

- the absolute value of GFR
- the absolute difference of GFR from the baseline
- the annual degradation (ml/min/1,73m²/year) of GFR during the 24 months

Proteinuria evolution

The evolution of proteinuria will be assessed as:

- the absolute value of proteinuria at 12 and 24 months
- the absolute difference of proteinuria from baseline at 12 and 24 months

Identification of prognosis markers of failure at 24 months:

Clinical, histological, and biological data (including PCR ratio, eGFR and mGFR, renal histological lesions) will be compared between patients with or without failure.

Comparison of side effects in each therapeutic group.

Comparison of life quality scale in each therapeutic group with SF36 scale at 12 and 24 months

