4.2 Description of research methodology

4.2.1 Experimental plan

Phase III, prospective, multicenter, randomized open-labelled study.

Included patients will be randomized according to a 1:1 ratio:

- early corticotherapy + RAS blockade (experimental group)

or

- RAS blockade alone (control group), with corticosteroids in case of failure at 6, 9, 12 or 18 months or in case of rapid deterioration of renal function at 2 months and proposed corticosteroids in case of failure at 4 months.

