5.2 Follow-up Visits (M2 to M18)

Follow-up consultations with a nephrologist or hospitalizations will be performed at months 2, 4, 6, 9, 12, 18 and 24 from D0.

A two days hospitalization with mGFR, serum creatinine and proteinuria evaluation and repeat renal biopsy will be performed at month 12. Only one day hospitalization is scheduled if biopsy is not performed, or only one consultation is scheduled if biopsy is not performed and mGFR is not measured.

A one-day hospitalization with mGFR, serum creatinine and proteinuria evaluation will be performed at month 24. Only one consultation is scheduled if mGFR is not measured.

At each consultation (M2, M4, M6, M9 and M18) or hospitalization (M12 and M24) will be performed:

- Medical interview evaluating compliance for treatments and lifestyle recommendations

- Clinical examination with sitting blood pressure measurement, checking for postural hypotension, weight measurement, general and cardiovascular examination, and ethnic origin.

- Biochemistry: plasma sodium, potassium, albumin, total proteins, bicarbonate, chlorure, fasting glycemia, total and LDL cholesterol, triglycerides, urea, uric acid, serum creatinine (enzymatic IDMS-traceable assay), C reactive protein. Urinary protein, creatinine, sodium and urea will be evaluated on a 24-hour urinary collection (or urinary sample except to M2 and M4), eGFR.

- Haematology: blood count.

Biochemistry and haematology analyses are associated with care so they can be obtained before the consultation from private practice laboratories.

- at the visit M12 and M24, SF36 scale and biological collection (blood and urine)

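### In this open-label trial, the protocol neither names the planned central biopsy re-read as the source of the month-12 histology endpoint nor masks that reader to treatment arm.

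*Protocol*

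**What the plan says.** Protocol section 4.2.1 describes the design as "Phase III, prospective, multicenter, randomized open-labelled study". Section 4.1.2 lists, among the secondary criteria, the proportion of patients in each arm with "persistent severe histological lesions in repeat kidney biopsy at 12 months". Section 9.2 has secondary endpoints compared by a Chi2 or Fisher test where they are categorical, with P below 0.05 counted as significant.

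Section 8 describes two readings. For patient inclusion, each histological criterion "will be scored by local pathologists". Then: "Secondarily, all renal biopsies will be re-evaluated" a posteriori, in one central pathology department. Only one analysis is tied by name to the a posteriori reading, namely the search for prognostic markers of failure at 24 months, which uses "renal histological lesions evaluated" in that way. On handling, section 8 says only: "Renal biopsy will be performed and processed according to local practices". Section 5.2 allows for a month-12 visit without a biopsy: "Only one day hospitalization is scheduled if biopsy is not performed".

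No section says which reading gives the month-12 endpoint, or that the reader is kept unaware of treatment arm.

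**The concern.** Lesion scoring is a visual judgement, and this endpoint turns it into a yes/no call. A reader who knows the arm can lean, without intending to, on borderline cases. The protocol itself supplies the direction: the rationale in section 2.3 cites regression of crescents, mesangial proliferation, segmental sclerosis and fibrosis after steroids. If the central reader knew who had early steroids, the lean would favour the experimental arm and feed directly into the between-arm comparison.

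What is at stake is the credibility of the month-12 histology comparison. The repeat biopsy is an invasive procedure added by the research (section 5.5), so its reading should be as free of this doubt as the design allows. Once slides have been read with the arm known, no later analysis document can undo it.

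**Working it through.** **1. The two readings side by side**

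| | Local reading | Central re-read |
|---|---|---|
| Stated purpose | Inclusion | All biopsies, a posteriori; named use is the 24-month prognostic markers |
| Biopsies covered | The qualifying biopsy | All, so month 12 as well |
| Timing against randomisation | Before: histological criteria are checked, then the patient is randomised (section 5.1) | After |
| Can the reader know the arm? | No, no arm exists yet | Not excluded by the text |
| Named as month-12 endpoint source? | No | No |

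The gap therefore concerns the central re-read only. It is the one reading that expressly covers month-12 biopsies, and it is neither designated for the endpoint nor masked.

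**2. The plan's own figure**

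The protocol gives no sample size, lesion rate or reading-error rate for histology. Its only calculation is for the primary endpoint (section 9.1: 60% against 35%, 80% power, two-sided 5%, 61 per group). With pooled variance and no continuity correction, mean rate 0.475:

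n = [1.96·√(2·0.475·0.525) + 0.8416·√(0.60·0.40 + 0.35·0.65)]² / 0.25² = (1.384 + 0.575)² / 0.0625 ≈ 61.4, so 62 per arm.

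Power at 61 is 79.7%. The stated 61 is reproduced to within one patient. It does not bear on this point, except that 61 is the most biopsies per arm that the planned sample can give.

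**3. How a differential reading would act (illustration)**

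Assumptions, none from the documents: true persistence p is the same in both arms (0.40 to 0.60); only the steroid arm is read more favourably; 61 biopsies per arm are read, or 45 if some are not done.

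With p₁ = p in controls, p₂ the rate as read in the steroid arm, p̄ their mean and d = p₁ − p₂:

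- c = 1.96·√[2p̄(1 − p̄)/n]
- s = √[(p₁(1 − p₁) + p₂(1 − p₂))/n]
- rejection rate = 1 − Φ((c − d)/s) + Φ((−c − d)/s)

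Worked case: p = 0.60, one tenth of persistent lesions called resolved, n = 61. Then p₂ = 0.54, d = 0.06, c = 0.1757, s = 0.0895. The rate is 1 − Φ(1.293) + Φ(−2.634) = 0.098 + 0.004 = 10.2%.

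| Assumed reading in the steroid arm | n = 61 | n = 45 |
|---|---|---|
| Same as control | 5% | 5% |
| 10% of persistent lesions called resolved, p = 0.40 | 7.4% | 6.7% |
| 10% called resolved, p = 0.60 | 10.2% | 8.8% |
| 10-point shift, 0.60 read as 0.50 | 19.8% | 15.8% |

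For the last row, exact binomial calculation gives 21% and 15%. A 10-point shift from 60% means that 0.10/0.60, or one in six, truly persistent cases is called resolved in one arm only. That is a strong lean.

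**4. What would shrink it**

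Under sections 4.2.1 and 7.4.1, controls can receive the same steroid course before month 12, after failure at month 4, 6 or 9 or rapid deterioration at month 2. A reader expecting improvement after steroids would then favour some controls too. The table ignores this, so it overstates the effect to the extent that rescue is used.

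**The case against.** The strongest reply is that silence is not evidence of bias. The central re-read is the only reading that expressly covers month-12 biopsies, so it is plausibly the intended endpoint source, and nothing says its reader will know the arm. A statistical analysis plan, not shown here, could name the reading. Section 2.2 also cites strong inter-observer reproducibility for the Oxford criteria.

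Most of this stands as a limit on the point. It does not remove it. An analysis plan can choose between readings, but concealing arm from a reader has to be arranged before the slides are read, so it belongs with study conduct. Reproducibility shows that readers agree with each other. It does not show that a reader is unaffected by knowing the treatment.

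A reader might infer several stronger things that the protocol does not support:

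- That the endpoint rests on local, unmasked scoring. Local scoring is stated for inclusion only and precedes randomisation, so arm cannot bias it.
- That the histological subgroups in section 9.2 are biased by allocation. They concern the primary outcome, and baseline lesion scores made for eligibility exist before allocation.
- That knowing baseline from month 12 biases the comparison by itself. Every month-12 biopsy in both arms is a follow-up biopsy, so that knowledge alone moves both arms alike.
- That histology ranks as the main secondary endpoint. Sections 3.2 and 4.1.2 list it unranked among others.

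**Conclusion.** The point holds in a narrow form. The protocol does not say that the planned central re-read supplies the month-12 histology endpoint, and it does not mask that reader to arm, although the trial is open-label and the rationale states which way lesions should move. The protocol leaves this route to bias open; it does not show that bias will occur.

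The size cannot be derived from the documents. The illustrative false-positive rates (about 7–10% under a mild differential reading at 61 per arm, about 15–21% under a 10-point shift from 60%) depend wholly on assumed persistence, assumed misreading and the number of biopsies read. They also leave out rescue steroids in controls. The primary endpoint in section 4.1.1 (proteinuria ratio, GFR, ESRD, transplantation, death) involves no biopsy reading, so the 24-month treatment comparison is unaffected. This is a cheap improvement to one secondary endpoint and not a threat to the trial's main conclusion.

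**What to change.** In section 8, under histological evaluation, state that:

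- the central re-read defines the month-12 histology endpoint;
- it is done on coded slides with treatment arm and centre concealed from the reader;
- where practical, biopsy date and sequence are concealed too, with baseline and month-12 slides mixed;
- local scores serve eligibility.

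The cost is the work of coding (and, where done, mixing) slides before a re-read that is already planned. No extra reader or biopsy is needed, and the sample size stays at 61 per group.

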9 STATISTICAL ASPECTS

9.1 Calculation of sample size

Given the results of previous studies, we assume that 60% of the patients in the control group will achieve the failure criteria at 24 months. We aim to obtain a decrease to 35% of failure with early corticotherapy (i.e in the experimental group). With 80% power and an 2-sided alpha risk equal to 5%, 61 subjects per group are required. Consequently, 122 patients will be included in this study.

9.2 Description of statistical methods to be used

All statistical analyses will be performed by Dr [name] (Paris Centre Clinical Research Department) using R software (http://cran.r-project.org).

Primary analyses will include all patients who underwent randomization and will be conducted on the intention-to-treat principle for efficacy outcomes and according to treatment received for toxicity end points. A per protocol analysis will be also performed, after exclusion of the subjects with at least one significant protocol deviation.

Descriptive analyses will be done for the two arms of treatment. Continuous variables will be summarized as mean (standard deviation) or median [range] and categorical variables as frequencies and percentages.

Primary end-point

Percentages of patient with failure at 24 months (as defined earlier) will be compared between groups using Chi2 test. Treatment effect will be presented as Relative Risk (RR) and its 95% CI.

Secondary end-points

Secondary efficacy and safety end points were analysed using Chi2 test (or Fisher's test if appropriate) and Student t test (or Wilcoxon test if appropriate).

To explore the emergence of any time-related patterns of response to treatment, means and 95% confidence intervals (CIs) for changes relative to baseline in proteinuria and GFR were plotted vs time from randomization until end of follow-up at 24 months. Means and 95% CIs for changes from baseline were compared at 6, 12 and 24 months using Student t test. In addition linear marginal regression models will be performed, if appropriate.

Three subgroups analyses are planned to explore whether the primary outcome results differed in particular groups of patients. Histological subgroups will be defined as the presence of mesangial proliferation or not, the presence of endocapilary proliferation or not and the presence of cellular or fibrocellular crescents or not. Log binomial regression models will be used for the subgroup analyses and will include terms for treatment group, subgroup, and the interaction between treatment group and subgroup. The interaction terms represent potential subgroup differences in treatment effects.

For efficacy and safety comparisons, P values of less than 0.05 were considered to indicate statistical significance.

The pharmacokinetics of corticosteroids will be evaluated by population approach. The population approach allows, from a small number of samples per subject, collected at variable times between drug intake and sampling, to estimate the pharmacokinetic parameters of the drug as well as the variability in the population. Individual pharmacokinetic parameters will be derived using Bayesian estimation from the population model. Association between individual exposures (i.e. through concentration, area under the curve) and treatment failure will then be investigated.

10 SAFETY ASSESSMENT - RISKS AND RESTRICTIONS ADDED BY THE RESEARCH

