It should be noted that in most therapeutic studies of IgAN, renal function was evaluated with creatinine-based formula. However, it has been demonstrated that this type of evaluation criteria (such as doubling-serum creatinine or estimated GFR evolution) can overlook significative variations of renal function in chronic nephropathies^{23, 24}. In fact, when annual GFR loss is calculated by using estimated GFR (eGFR) (MDRD formula) or measured GFR (mGFR), GFR decline is similar between both methods in only 60% of cases²³. Other cases show difference between both methods of more than 2 ml/min/1,73m²/year (whereas mean GFR decline of IgAN with oxford criteria is approximately 5 ml/min/1,73m²/year) ^{12,13,23}. Then eGFR decline should be interpreted with caution in chronic nephropathies, including IgAN.

Nephroprotection

Treatments inhibiting the renin angiotensin system (RAS), with strict blood pressure and proteinuria goals, have a major role in limiting the progression of $IgAN^{25,26}$. In fact, in a Spanish study, RAS blockade allowed a reduction from 91% to 55% of proportion of patients with doubling serum creatinine after 7 years of follow-up²⁷. Current recommendations include blood pressure target < 130/80mmHg and proteinuria < 0,5g/d (as recently validated by the VALIGA study²¹). It should be noted that these recommendations were not reached in previous therapeutic studies^{25,26}. About 60% of patients do not respond to these therapies after 3 months of follow-up, according to a recent Asiatic serie²⁸. Then, expert opinion supports the use of corticosteroids in patients with progressive disease despite RAS inhibition^{25,26}, in a 2-step strategy (initial RAS inhibition, then corticosteroids therapy).

Corticosteroids

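### Analysing toxicity by treatment received can undo randomisation, because failing controls are given the experimental steroid course as planned rescue

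*Protocol*

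**What the plan says.** Protocol 9.2 sets two bases for the primary analyses: the "intention-to-treat principle for efficacy outcomes and according to treatment received for toxicity end points". It does not say how a control who takes rescue steroids is to be classed. The same section tests secondary efficacy and safety end points with Chi2 or Fisher tests and t or Wilcoxon tests at the 0.05 level, and mentions no allowance for exposure time.

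Protocol 4.1.2 gives the safety criterion as "Comparison of side effects in each therapeutic group".

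Protocol 4.2.1 defines the control strategy as "RAS blockade alone (control group), with corticosteroids in case of failure at 6, 9, 12 or 18 months", with further provision at months 2 and 4. Section 7.4.1 gives the detail:
- Month 2: steroids "should be administred in case of rapid deterioration of renal function", meaning eGFR below 70% of the initial value.
- Month 4: "rescue corticosteroid treatment (4 months of treatment, same protocol of experimental group) could be administred in case of failure", so it is optional.
- Later visits: "At 6, 9, 12, or 18 months, rescue corticosteroid treatment (4 months of treatment, same protocol of experimental group) should be administred" on failure by proteinuria or eGFR.

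Each trigger needs a confirming second sample.

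**The concern.** A safety set defined by treatment received suits the occasional dosing error or patient who never starts treatment. Here steroids in controls are expected, and what triggers them is a poor renal course. If receiving rescue moves a control to the steroid side, three things follow.

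- The groups are formed by outcome after randomisation, so they no longer differ only by treatment.
- A whole patient is moved, including events before the first steroid dose. A control rescued at month 18 would count as steroid-treated although about 18 of 24 months were free of steroids.
- The renal triggers overlap with recorded adverse events. Section 10.3 requires all adverse events in the CRF and lists acute renal failure, nephrotic syndrome and high blood pressure as natural evolution of the disease. Controls with such events are more likely to be among those rescued.

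The benefit-risk conclusion would then set a randomised efficacy estimate beside a confounded harm estimate. Tolerance is a secondary objective (3.2), but the treatment has potentially severe side effects by the protocol's own account (2.2), and there is no DSMB (10.7).

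**Working it through.** **Arm size.** Section 9.1 gives 61 per group for 60% versus 35% failure, 80% power and two-sided 5%. This reproduces: 61.3 by the arcsine formula and 62 by the pooled-variance formula without continuity correction. The sample size is not in question; 61 is used below only as the arm size.

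**Rescue rate, s.** Not stated. The nearest figures are in 2.2, "About 60% of patients do not respond to these therapies after 3 months of follow-up", and in 9.1, 60% control failure at 24 months. Both are proxies: the first is 3-month non-response in a cited series, the second uses a different failure definition and is assessed after any rescue. A range is therefore shown.

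**Group sizes if rescued controls are reclassified.** No-steroid set = 61 × (1 − s). Steroid set = 61 + 61 × s. Everyone in the experimental arm is taken to start steroids. The last column is √(1/n₁ + 1/n₂) divided by √(2/61), the standard error of a risk difference at a common event rate relative to 61 versus 61.

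| Rescue rate | Steroid vs no steroid | Rescued controls as share of steroid set | Relative standard error |
|---|---|---|---|
| 40% | 85 vs 37 | 24/85 = 28% | 1.09 |
| 50% | 92 vs 30 | 31/92 = 34% | 1.16 |
| 60% | 98 vs 24 | 37/98 = 38% | 1.26 |
| 80% | 110 vs 12 | 49/110 = 45% | 1.68 |

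**Selection with no steroid effect.** Assume that:
- rescued controls are the non-responders;
- the experimental arm holds the same share s of such patients, by randomisation;
- non-responders have k times the event risk a of responders.

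The values of k are assumptions, not figures from the protocol. Then:

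- experimental risk = a(1 − s + sk), and the same in the control arm, so the randomised RR is 1.0;
- as-treated RR = [(1 − s + sk) + sk]/(1 + s) = (1 − s + 2sk)/(1 + s).

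Results:
- s = 0.6, k = 1.5: (0.4 + 1.8)/1.6 = 1.38
- s = 0.6, k = 2: (0.4 + 2.4)/1.6 = 1.75
- s = 0.4, k = 1.5: (0.6 + 1.2)/1.4 = 1.29
- s = 0.4, k = 2: (0.6 + 1.6)/1.4 = 1.57

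Check with a = 0.10, k = 2, s = 0.6: experimental risk is 0.4 × 0.10 + 0.6 × 0.20 = 0.16. The steroid set has (61 × 0.16 + 36.6 × 0.20)/97.6 = 0.175, against 0.10 in the no-steroid set, giving 1.75.

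**The opposite bias, by randomised arm.** Suppose steroids add an absolute risk d to anyone who takes them, early or as rescue. The difference between arms over full follow-up is d − sd = (1 − s)d: 0.4d at 60% rescue and 0.6d at 40%. Comparison by arm estimates the harm of early against deferred steroids, not of steroids against none.

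**The case against.** The strongest reply is that 9.2 never says rescued controls change group. Section 4.2.1 makes rescue part of the control strategy, so a rescued control has received the assigned treatment. Treatment received could mean the regimen initially started, in which case it differs from randomisation only for patients who got the wrong regimen or none. Section 4.1.2 fits that reading, and a SAP may define the term. This stands as a possible reading, so reclassification cannot be presented as the settled plan, and 4.1.2 conflicts with 9.2 only if reclassification is meant. But the protocol itself sets the treatment-received basis against intention to treat, and under the plain reading that basis can bias the result. The two readings can give different tolerance conclusions, and the trial is open-label.

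Three stronger inferences are tempting and not supported:

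- *That the no-steroid group would hold only RAS responders.* It would be mainly responders. It could also hold controls who failed at the optional month-4 step and left before month 6, controls whose first failure is at month 24, and controls who refused rescue or left early. Experimental patients who never started steroids could be there too. So could controls above the month-24 limit of 0.5 g/g who never met the looser rescue threshold.
- *That rescue picks out the sickest controls.* Entry requires PCR above 0.75 g/g (6.1), and rescue from month 4 is triggered above the same value, so a patient merely unchanged from baseline qualifies.
- *That most controls will be rescued.* This is plausible from the two 60% figures, but it is not stated.

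It is also fair to say that comparison by randomised arm has its own bias, toward no difference, when rescue is common. That holds, and it shapes the fix.

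**Conclusion.** The point holds conditionally. If treatment received classes rescued controls as steroid-treated, the toxicity comparison is not randomised, its no-steroid side is small and mainly responders, and it departs from the comparison by therapeutic group in 4.1.2. At 40% to 60% rescue the groups would be about 85 versus 37 to 98 versus 24. An as-treated RR of about 1.3 to 1.75 could then appear with no steroid effect. The group sizes rest on a proxy rescue rate and the RRs also on assumed risk ratios of 1.5 to 2, so they show the mechanism and its possible scale and do not forecast the result. If the phrase means treatment initially started, the bias does not arise and only the wording needs repair. The primary end point and sample size are unaffected. Severity: should-fix; a cheap improvement.

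**What to change.** In 9.2, state that the main safety comparison is by randomised arm (or by treatment initially started), with rescued controls kept in the control arm, and align the wording with 4.1.2.

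Pair this with a required companion analysis: adverse event rates per patient-month in steroid-exposed and unexposed time, with the first steroid dose as a time-varying exposure, so that events before rescue are not charged to steroids. The companion is needed because the comparison by arm dilutes true steroid harm as rescue becomes common. It is itself not randomised and should be read as supportive.

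The cost is a sentence or two in 9.2, with no change to sample size, visits or treatment. It does require that the e-CRF capture steroid start dates in both arms and onset dates for all adverse events. That is likely but not stated in the protocol, and should be confirmed.

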4.2.4 Randomization

Randomization will be stratified according to centre and will use permutation blocks, the size of each being not available to clinicians.

Centralised randomization will be carried out by the investigator after inclusion using the cleanWeb system (Telemedecine).

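### The planned Chi2 and change-score t tests are valid, but they leave out baseline PCR and GFR and so give away precision that costs almost nothing to recover

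*Protocol*

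**What the plan says.** For the primary endpoint, section 9.2 says "Percentages of patient with failure at 24 months (as defined earlier) will be compared between groups using Chi2 test", with the effect given as a relative risk and 95% CI. For GFR and proteinuria over time the same section says "Means and 95% CIs for changes from baseline were compared at 6, 12 and 24 months using Student t test".

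No treatment comparison names a centre or baseline term. Two other kinds of model appear. Log-binomial models serve only the three histological subgroup analyses. Linear marginal models are to be added conditionally, for the longitudinal continuous data, with no covariates named.

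On design, section 4.2.4 says "Randomization will be stratified according to centre and will use permutation blocks". Section 8 relies on this for the different GFR measurement methods: "Given that the randomization is stratified by centre, the difference between the mGFR techniques should not have a major effect in data interpretation".

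Baseline GFR and urinary protein and creatinine are scheduled at D0 (sections 5.1 and 5.4). Section 2.2 lists renal insufficiency and proteinuria among the few reproduced prognostic factors. Section 8 lists initial proteinuria and initial eGFR as candidate markers of failure at 24 months.

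**The concern.** Section 9.2 names the tests itself, so this is a stated choice and not a detail left to the SAP. It sets aside baseline information that bears directly on the endpoint.

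- **PCR.** Entry requires PCR above 0.75 g/g (section 6.1), and failure is a fixed cut at 0.5 g/g (section 4.1.1). As an illustration, a patient who starts at 0.8 must fall by (0.8 − 0.5)/0.8 = 38% to escape failure. One who starts at 3.0 must fall by (3.0 − 0.5)/3.0 = 83%.
- **GFR.** Failure is a value below 80% of baseline or a loss above 10 ml/min/1.73m². The two rules cross at a baseline of 50, where 20% equals 10 ml. At 25 the allowed loss is 5 ml (20%), and at 100 it is 10 ml (10%).

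At stake is the width of the confidence interval, and how well the result stands up to a chance difference between arms in baseline PCR or GFR. Centre is a separate and smaller matter: stratified allocation that is not reflected in the analysis makes the standard error too large when centres differ.

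**Working it through.** **1. The plan's own figure.** Inputs from section 9.1: 60% versus 35% failure, 80% power, two-sided 5%. The plan states "With 80% power and an 2-sided alpha risk equal to 5%, 61 subjects per group are required".

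Usual pooled-variance formula, mean proportion 0.475:

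n = [1.960·√(2·0.475·0.525) + 0.842·√(0.6·0.4 + 0.35·0.65)]² / 0.25² = [1.384 + 0.575]² / 0.0625 = 61.4, rounded up to 62.

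The arcsine formula gives 61.3. Power at 61 per arm is 79.7%. The stated size is reproduced, on the basis of an unadjusted comparison of two proportions.

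**2. Baseline adjustment, primary endpoint.** The protocol gives no strength for baseline PCR or GFR, so a range is assumed. Simulation: 61 per arm, 60% versus 35%, one baseline score, 4000 trials per row, Chi2 against a logistic model standardised to a marginal effect. Monte Carlo error is √(0.81·0.19/4000), about 0.6 points.

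| Assumed latent correlation | Chi2 power | Adjusted power | Difference (points) |
|---|---|---|---|
| 0 | 81.3% | 80.8% | −0.5 |
| 0.3 | 82.2% | 83.4% | +1.2 |
| 0.5 | 81.1% | 87.0% | +5.9 |
| 0.6 | 81.0% | 89.6% | +8.6 |

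Type I error was similar for both methods (4.7% to 5.7%). A second simulation (2000 trials per cell, Monte Carlo error about 0.9 points) used plain logistic regression and gave adjusted versus Chi2 power as follows:

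- covariate not prognostic: 80.4% versus 81.6%
- log odds ratio 0.5 per SD: 83.0% versus 82.5%
- log odds ratio 1.0 per SD: 85.8% versus 81.4%

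On the latent scale, β/√(β² + 3.29), these log odds ratios correspond to correlations of about 0.27 and 0.48, so the two runs agree.

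In the first simulation, arms differed on the score by more than 1.5 standard errors in about 13% of trials. Within those trials, at correlations 0.5 and 0.6, the Chi2 false-positive rate was 10.9% and 13.1%, against 5.6% and 5.2% adjusted.

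**3. Continuous endpoints.** With equal variance σ² at baseline and follow-up and correlation ρ, the change-score variance is 2σ²(1 − ρ) and the ANCOVA variance is σ²(1 − ρ²). The ratio of ANCOVA to change score is (1 + ρ)/2:

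- ρ = 0.5: 0.75, a 25% reduction
- ρ = 0.7: 0.85, a 15% reduction
- ρ = 0.9: 0.95, a 5% reduction

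No ρ is given in the protocol.

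**4. Centre.** There are 122 patients in 27 centres, or 122/27 = 4.5 per centre. Simulation: 2000 trials per cell, blocks of 4 within centre (assumed; the size is not given), no baseline covariate. The intraclass correlation is SD²/(SD² + 3.29).

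| Between-centre SD (logit) | ICC | Chi2 type I error | Model SE / true SD of risk difference (null) | Chi2 power | CMH power by centre |
|---|---|---|---|---|---|
| 0 | 0 | 5.2% | 0.0897 / 0.0900 | 81.6% | 77.6% |
| 0.5 | 0.07 | 5.0% | 0.0897 / 0.0883 | 82.3% | 80.2% |
| 1.0 | 0.23 | 3.9% | 0.0895 / 0.0847 | 80.4% | 82.2% |

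At SD 1.0 the standard error is 0.0895/0.0847 = 1.06 times the true value, about 6% too wide. A separate run of 4000 trials gave type I error of 4.1% at SD 1.0. Conditioning on 27 strata costs 4.0 and 2.1 points at SD 0 and 0.5, and gains 1.8 points at SD 1.0.

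**The case against.** The strongest reply is that nothing here is an error. Omitting baseline covariates from a randomised comparison leaves the Chi2 and its interval valid. The trial was sized for that kind of comparison and gets the power it claims. Chance imbalance is already counted in the overall 5% error rate. All of this stands. The conditional error rates in step 2 describe an unlucky subset of trials, not an inflated test.

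The gain also rests on assumed correlations. Entry criteria truncate the baseline range, and the GFR components are already relative to each patient's own value. This stands as a limit on the size of the gain, whose lower end is nil. It does not remove the dependence of the PCR cut, or of the two GFR rules, on the starting value.

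For the secondary endpoints, section 9.2 allows a Wilcoxon test where suitable, adds conditional marginal models, and introduces the t tests on change as exploratory. That lowers the weight of the point. Section 4.1.2 defines proteinuria evolution as an absolute value and an absolute difference, so replacing it by log PCR would change the stated quantity. ANCOVA on the original scale would not.

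A reader might infer that section 8 is contradicted because centre is dropped from the analysis. The protocol does not support that: stratified allocation balances measurement methods between arms by design, whether or not centre enters the model.

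Finally, the simulations used one baseline score without a centre term. The full model with two covariates and a random centre effect was not tested.

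**Conclusion.** The point holds as one of lost precision, of minor to moderate weight. Adjustment for baseline PCR and GFR would add about 0 to 9 points of power on the primary endpoint, for an assumed latent correlation of 0 to 0.6. For GFR and proteinuria it would cut variance by 5% to 25%, for an assumed correlation of 0.9 down to 0.5. If the covariates prove uninformative, the cost is about nil.

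Two stronger readings are tempting and unsupported. One is that the trial is biased or misses its stated power: the Chi2 is valid and reaches 79.7% at 61 per arm. The other is that the error bars are wrong in general: only the omission of centre affects them, only conservatively, and only if centres differ materially. A type I error as low as 2.6% appeared only at an assumed between-centre SD of 1.5 logits (ICC 2.25/5.54 = 0.41), and nothing in the protocol suggests differences that large.

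**What to change.** Before the data are seen:

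- **Primary.** Model failure at 24 months on treatment, baseline PCR and baseline GFR, standardised to a marginal relative risk with a robust 95% CI. Name the baseline values (the D0 measurements). Keep the Chi2 as a sensitivity analysis.
- **GFR and proteinuria.** Compare follow-up values by ANCOVA on the baseline value in place of t tests on change. Log PCR can be an optional supplement, labelled as a different quantity.
- **Centre.** Do not condition on 27 fixed strata at about 4.5 patients each. Carry centre as a random intercept, or with small centres pooled, in a sensitivity analysis.

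The cost is wording and slightly more programming. No new data or patients are needed.
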